8.6 VITAL SIGNS AND PULSE OXIMETRY

Vital sign data [systolic blood pressure, diastolic blood pressure, pulse, respiration rate, temperature, mean arterial pressure (MAP)] will be collected at each study time point, and pulse oximetry/FiO₂ data will be collected through Study Day 7. Summaries will be prepared for each time point as well as the changes from baseline (i.e., last observation prior to Randomization). Additional summaries of changes relative to ELAD start date/time will be provided for subjects in the ELAD treatment group. For comparison purposes, changes relative to End of Study Day 2 (± 6 hours) will be summarized for the Control treatment group. Proportion of subjects with MAP <60 mmHg vs. ≥60 mmHg will be presented by study group. No inferential statistical analyses will be performed for the summaries of vital sign data.

8.7 CONCOMITANT PROCEDURES

Concomitant procedures will be coded using MedDRA version 18.1, similar to the approach for coding adverse events. Concomitant procedures including concomitant therapies (e.g., intubation, tracheostomy, CVVH/CVVHD, arterial line) are those administered any time between Randomization and through Study Day 91. Proportions of subjects by coded procedure administered during treatment and post-treatment periods will be presented by treatment group. No inferential statistical analyses will be performed.

8.8 HOSPITALIZATION SUMMARY

The number of days alive and out of the hospital during the first 90 days post-randomization will be summarized by treatment group. This will be based on the date of initial hospital admission (including referral hospital where applicable) and the date of hospital discharge for this hospital admission. Mean period of hospitalization will be compared between ELAD and Control.

Additionally, the proportion of subjects by initial discharge location out of the hospital will be summarized by treatment group.

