5.5.5 Evaluations on Study Day 63 and Study Day 91 (+5 days)

On Study Days 63 and 91, the following evaluations will be completed for all subjects:

- Vital signs (blood pressure, heart rate, respiration rate, and temperature)
- Physical examination (performed by a Physician, Physician Assistant, or Nurse Practitioner if within the scope of practice for institution)
- Encephalopathy stage [West Haven Criteria, performed by a study physician, Physician Assistant, or Nurse Practitioner if within the scope of practice for institution (Refer to [Appendix A](#))] unless subject is sedated

- Laboratory evaluations: BUN, creatinine, glucose, sodium, potassium, chloride, carbon dioxide (or bicarbonate), calcium, magnesium, phosphate, ALT, AST, bilirubin (total/direct), albumin, total protein, alkaline phosphatase
- Additional required laboratory evaluations: ammonia, lactate, α -fetoprotein, and LDH
- CBC: WBC count, hematocrit, hemoglobin, and platelets
- PT, PTT, and INR
- Blood collection for outside analysis (consented subjects at participating centers only) (See [Section 5.6.3](#))
- Documentation of all transfers, discharges, readmissions and admissions within or outside institution. All emergency room visits must also be documented
- MELD score will be autocalculated in accord with [Section 5.2.4](#)
- Assessment of concomitant medications
- Concomitant therapies (e.g., intubation, tracheostomy, CVVH/CVVHD, arterial line) will be monitored continuously from Randomization and recorded
- Assessment of adverse events
- Follow up Dietary consult (including weight)
- EQ-5D-5L Quality of Life (QOL) questionnaire ONLY if subject is being discharged or if it is the Study Day 91 visit

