5.5.7 Evaluations Following Discharge

A post-hospital discharge evaluation is any study-defined subject evaluation that takes place following discharge from the hospital where study treatment was conducted. It is defined the same across both treatment arms.

All study-scheduled, post-hospital discharge follow-up evaluations will be conducted by an Investigator who is blinded to the subject's treatment assignment unless the subject is currently hospitalized. Inpatient evaluations can be carried out by any member of the study team. For clarification, study-defined subject evaluations that would be carried out by the Blinded Investigator would include the physical exam, encephalopathy assessment (West Haven Criteria), assessment of AEs and SAEs, and recommendation of management of the subject's care (inclusive of recommendations for hospital readmission when applicable).

Study participants will be instructed not to tell the Blinded Investigator conducting the post-discharge evaluations whether or not they received ELAD treatment. This information must be reinforced to all subjects after treatment and again upon hospital discharge. They must be instructed to NOT divulge their study arm (treatment group) to any study personnel who were not a part of their care team while during the treatment phase of the study.

Decisions for hospital readmission are to be made independently of knowledge of the subject's treatment group.

Payments will be made to the subject for each post-discharge study site visit and home visit if allowed by the individual site/IRB/EC and/or regulatory agency.

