7.1.4 Assessment of Potential Bias due to Treatment Group Assignment

VTL-308 is an open-label study. While every effort has been made in the study protocol to minimize the effects of post-treatment differences in investigator evaluation, medical care and subject behavior, there is a potential that differences in these factors may be associated with treatment group assignment, and that these differences might influence outcomes. An evaluation of the proportion of survivors at Study Days 28 and 91 will be carried out to determine whether these differences had any impact on study outcome. Parameters assessed will include, but not be limited to, the following:

- Alcohol use post-discharge. This will be evaluated based on either a PEth result of >20 ng/mL (evidence of moderate or heavy alcohol consumption) or any self-report of alcohol use post-discharge (note: a positive PEth result will supersede a self-report of no alcohol use);
- Length of Initial ICU Stay (<Median and ≥Median), defined as the first ICU discharge date minus ICU admission date plus 1, if the admission date is after randomization. If the admission date is before randomization, then the length of stay will be the discharge date minus randomization date plus 1. If the discharge date is missing and the subject died, the death date will be used;
- Length of Initial Hospital Stay (<Median and ≥Median), defined as the hospital discharge date minus randomization date plus 1. If discharge date is missing and the subject died, the death date will be used;
- Steroids Use Post-randomization (Yes/No);
- Steroids Use Post-randomization for <7 days (Yes/No);

- Steroids Use Post-randomization for ≥ 7 to < 14 days (Yes/No);
- Steroids Use Post-randomization for ≥ 14 to < 28 days (Yes/No);
- Steroids Use Post-randomization for at least 28 days (Yes/No);
- Concomitant heparin use within the first 10 days of the study (Yes/No);
- For the ELAD group only, ELAD treatment duration dichotomized based on < 72 hours vs. ≥ 72 hours. This analysis will be based on total ELAD treatment duration inclusive of any time off treatment (i.e., final stop date/time of treatment, defined as the time at which the ultrafiltrate pump is switched off for the last time – initial start date/time of treatment, defined as the time at which the ultrafiltrate pump is switched on for the first time). Additional analyses of ELAD treatment duration are described in [Section 8.2](#) and [8.10.1](#).

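### SAP 8.8 derives days alive and out of the hospital from the initial admission and its discharge only, so readmission days within the 90-day window are counted as out of the hospital

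*SAP*

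**What the plan says.** SAP 8.8 (Hospitalization Summary) names the measure: "The number of days alive and out of the hospital during the first 90 days post-randomization will be summarized by treatment group". The next sentence gives the derivation. It opens "This will be based on the date of initial hospital admission (including referral hospital where applicable" and pairs that date with "the date of hospital discharge for this hospital admission". A third sentence adds a second quantity: "Mean period of hospitalization will be compared between ELAD and Control". The section gives no rule for death, a missing discharge date or later admissions, and it names no test.

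The only other hospital-stay measure in the SAP is the length of initial hospital stay in 7.1.4, "defined as the hospital discharge date minus randomization date plus 1". That section substitutes the death date when the discharge date is missing. It too stops at the first discharge.

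The protocol asks for more than these rules use. Sections 5.5.1, 5.5.4 and 5.5.5 each list "Documentation of all transfers, discharges, readmissions and admissions within or outside institution", and the Subject Location item in Tables 2 and 3 carries the same requirement through Study Day 91. Section 5.5.7 anticipates readmission and guards it against bias: "Decisions for hospital readmission are to be made independently of knowledge" of treatment group.

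**The concern.** The measure is defined over a 90-day window, but its derivation looks at one admission and one discharge. A subject can leave the hospital early, return for weeks, and score the same as a subject who never returned. The number reported would then not be what its name says.

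The trial is open-label, and the protocol takes steps to keep readmission decisions independent of treatment group. A summary of hospital-free time that leaves readmission out drops the part of the hospital course that those steps protect. If readmission differed between arms, the arm with more of it would look better on this measure than it should.

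**Working it through.** **Plan's own figure.** The documents state no expected value for this measure, so there is nothing to reproduce. The check is a reading of the rule followed by day counts.

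**Inputs from the documents.** The window is 90 days from randomization (SAP 8.8). The dates used are the initial admission and the discharge from that admission (SAP 8.8). Readmissions are documented through Study Day 91 (Protocol 5.5.1, 5.5.4, 5.5.5; Tables 2 and 3).

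**Inputs assumed.** The discharge days, readmission days, readmission proportions and death day below are illustrative, because the documents give none of them. SAP 8.8 has no death rule, so counting stops at death, as the word alive implies.

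**Formulas.** Subjects are in the hospital when randomized, so:

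- Rule as written: min(90, death day) − initial discharge day.
- Measure as named: 90 − (index inpatient days after randomization + readmission days in the window) − days dead in the window.

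| Assumed case | Rule as written | Measure as named |
|---|---|---|
| Discharged day 14, alive at day 90, no readmission | 90 − 14 = 76 | 90 − 14 − 0 = 76 |
| Same, 10 readmission days | 76 | 90 − (14 + 10) = 66 |
| Same, 30 readmission days | 76 | 90 − (14 + 30) = 46 |
| Discharged day 14, 20 readmission days, died day 60 | 60 − 14 = 46 | 90 − (14 + 20) − 30 = 26 |

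In every row the difference equals the subject's readmission days in the window. That follows from the two formulas and does not depend on the values chosen.

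**Mean error per arm** = proportion of subjects readmitted × mean readmission days. The assumed ranges give 0.10 × 5 = 0.5 days to 0.50 × 20 = 10 days.

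**Between-arm error** = difference in proportion readmitted × mean readmission days, taking the same mean in both arms. Equal proportions give 0. With 40% against 20%, it is 0.20 × 5 = 1 day to 0.20 × 20 = 4 days, in favor of the arm with more readmission. Swapping the arms reverses the sign. Nothing in the documents says which case applies.

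**The admission date.** It appears in neither formula. Days out of the hospital after randomization depend on discharge, readmission and death, so an admission date before randomization does not change the 90-day count. It matters only for the mean period of hospitalization.

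**The case against.** The best defense is that the date rule in SAP 8.8 was meant to define the mean period of hospitalization in the following sentence. An admission date, including one at a referral hospital, is what a length of stay needs and a post-randomization count does not. On that reading the days-out measure is under-specified rather than wrongly specified. The reading is possible, but the sentence follows the days-out measure and, as written, refers to it. Even if the other meaning was intended, the days-out measure would have no derivation and 8.8 would still need rewriting.

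A reader might go further and infer any of the following. The documents do not support them.

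- *Readmission differences would be missed entirely.* In-patient hospitalization is a seriousness criterion (Protocol 9.2), and serious events are collected through Study Day 91 (Protocol 9.4). Serious treatment-emergent events are tabulated by period and listed (SAP 8.3), with separate tables for infection, fluid and bleeding events (SAP 8.3.1). SAP 8 also promises listings of all CRF data. Not every readmission has to be a serious event, and none of these tables counts inpatient days, but much of the signal appears elsewhere.
- *The miscounted days were spent at home.* SAP 8.8 says only out of the hospital. Protocol 5.5.7 allows discharge to a skilled nursing facility, hospice or rehabilitation facility.
- *The early admission date biases the 90-day count.* It does not enter that count, as shown above.
- *The mean-stay comparison rewards early death.* A death in hospital can shorten a stay, and 8.8 has no rule for it. But the SAP draws no conclusion of benefit from a shorter stay, and overall survival is the primary endpoint. Showing deaths beside the stay deals with this.

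It is also fair to say that this is a descriptive item in the safety section, outside the primary, secondary and exploratory objectives listed in SAP 1.2, with no alpha attached.

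**Conclusion.** The point holds in a limited form. Followed as written, SAP 8.8 gives the wrong value for the measure it names in any subject readmitted within the window. The error is always upward and equals that subject's readmission days. Its mean size and between-arm direction are unknown. The range of 0.5 to 10 days per arm rests wholly on assumed readmission rates and durations and should not be quoted as an estimate for this trial. The primary overall survival analysis, its significance level and the sample size are untouched. The conclusion relies on the literal reading of the derivation sentence; on the other reading, the defect is a missing derivation and the remedy is the same.

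**What to change.** Rewrite SAP 8.8 as two separate summaries.

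1. Days alive and out of the hospital = 90 minus all inpatient days from randomization to Day 90 (index stay plus every documented readmission) minus days dead in the window. State the day-count convention, how a transfer between hospitals is treated, and the rules for missing dates and for loss to follow-up before Day 90.
2. Index length of stay as its own descriptive summary, from a stated start date, for all randomized subjects, with in-hospital deaths shown alongside. Restricting it to subjects discharged alive would condition on a post-randomization outcome and break the randomized comparison. The Safety population in SAP 3.4 already takes in all randomized subjects, grouped by treatment received, so no new analysis set is needed.

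A rank test between arms is optional; the derivation is the essential change.

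The cost is SAP wording and programming. The protocol already requires readmissions to be documented. It does not set out the eCRF fields, so the sponsor should confirm that admission and discharge dates are captured for each readmission.

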8.9 HOME HEALTH CARE SUMMARY

After hospital discharge, home visits are conducted on a weekly basis up to Study Day 91 for all subjects to administer questionnaires on self-reported alcohol use and treatment services utilization, along with collection of an alcohol biomarker (PEth test). The proportion of subjects consuming alcohol post-discharge will be summarized by treatment group based on the following criteria:

- Subjects who reported any standard drink taken at any time post-hospital discharge;
- Subjects with a PEth lab results >20 ng at any time post-hospital discharge.

In order to evaluate differences between the treatment groups on the above recidivism variables, a Chi-squared test will be performed.

All home health care summary data will be listed.

8.10 EXPLORATORY ANALYSIS

Exploratory safety analyses will be based on ELAD System performance, therapeutic interventions of interest and administration of concomitant pharmacotherapies of interest.

For ELAD-treated subjects, analyses specific to ELAD treatment will be conducted based on the ELAD System performance files (PERF), the ELAD Specialist CRF, and the ELAD cartridge manufacturing data. These analyses will include summary statistics (e.g., N, mean, median, SD, proportions, as appropriate) for average fluid administration per day, glucose administration per hour and overall, number of component exchanges per subject per treatment, number of subjects with component exchanges by component along with reason for exchange and number of total exchanges for components of interest, estimated blood loss per subject due to component exchange and non-component exchange, and ELAD cartridge parameters including oxygen utilization rate (OUR) per minute, albumin production rate (mg/day), transferrin production rate (mg/day), glucose consumption per hour, age of cartridge, time to flush the cartridge, and time from cartridge shipping to treatment start.

A listing of subjects who were not on steroids at randomization will be presented along with the reason why steroid administration was not initiated. Listings will also be presented for blood cultures, sputum cultures, peritoneal fluid cultures and lab test results, and urine cultures.

8.10.1 ELAD Treatment Duration

ELAD treatment duration based on PERF data will be summarized. The duration is defined as total number of hours during which the ultrafiltrate pump is on. It will also be categorized into 3 groups: <72 hours, 72 hours to <96 hours, ≥96 hours. The counts of subjects in each category will be reported.

8.10.2 Total Amount of Ultrafiltrate

The total amount of ultrafiltrate (L) generated for each subject per day and overall by treatment, which is defined as the sum of the volume of ultrafiltrate delivered for each minute of perfusion (based on PERF data) will be summarized.

8.10.3 Blood Loss Associated with Blood Circuit Line Component Exchanges

A listing of subjects with a total blood loss volume ≥ 250 mL associated with blood circuit line component exchanges during ELAD treatment will be provided.

The total blood loss volume ≥ 250 mL associated with component exchanges during ELAD treatment was selected since this blood volume is equivalent to approximately one-half unit of packed red blood cells and this blood loss volume was deemed to be clinically significant.

8.10.4 Total Amount of Oxygen Utilization by Cell Cartridges

The total amount of oxygen utilization by the cell cartridges (mmHg·L) will be calculated by multiplying the amount of ultrafiltrate delivered each minute by the difference in oxygen partial pressure for each minute and then by calculating the sum of these values for each subject per day and overall by treatment. This will be summarized using descriptive statistics.

8.10.5 Fluid Administration Associated with Component Exchanges

A listing of subjects with a fluid volume that is \geq the median volume of fluid administered with component exchanges during ELAD treatment will be provided.

8.10.6 Correlation Analyses

Correlational analyses will look at the relationship between the age of the ELAD cartridge vs. oxygen and glucose consumption during treatment, as well as total blood loss and the total number of component exchanges.

9 DATA QUALITY ASSURANCE

Training was provided for the investigators and study coordinators at an investigator meeting held prior to initiation of the study. Site initiation visits for training and orientation of site personnel will be held at all sites prior to opening the site for enrollment. These meetings and visits will include training on completion of the eCRFs. Manuals will be provided to describe handling of laboratory samples, collection of the PEth alcohol test, study site responsibilities regarding home visits, and responsibilities of the home nurse.

The conduct of the study will be closely monitored by representatives of the Sponsor to verify adherence to ICH GCP guidelines and applicable standard operating procedures. Site monitoring visits will occur periodically during the course of the study, generally every 6 weeks or more frequently as needed.

Data management activities for this study will be performed by VTL and Axiom Real-Time Metrics (Axiom). Edit checks and review processes will be performed until all data clarifications are resolved. The data will be exported as SAS datasets. After all data clarifications are resolved and subject evaluability determined, the database will be locked. Synteract HCR will use the final SAS data for statistical analysis.

All SAEs will be reported directly by sites to the Axiom Pharmacovigilance team using a CRF designed to capture all SAE information. Axiom will be responsible for following up to ensure completeness of information. Axiom and VTL's medical monitor will work together to confirm that the event qualifies as an SAE, and to determine-if the SAE is a suspected unexpected serious adverse reaction (SUSAR). All information will be maintained in the Axiom Electronic Data Capture (EDC) database.

Narratives will be written for each randomized subject. All clinical details that are summarized in the narratives will be cross-checked against the final tables and listings to make sure that the clinical data reported in the clinical database are in agreement with the same clinical data presented in the narratives.

10 SOFTWARE AND VERSIONS

All analyses, data listings, tables, and graphs will be produced using SAS®, Version 9.2 or higher. MedDRA Version 18.1 will be used to code all adverse events.

Appendix A Standards of Care Compliance Assessment

The questions to assess compliance to the standards of care (SOC) for nutrition, steroids, ascites, gastroesophageal varices, hepatic encephalopathy, hepatorenal syndrome, hyponatremia, spontaneous bacterial peritonitis and hepatic hydrothorax are listed for each medical problem (ascites, gastroesophageal varices, hepatic encephalopathy, hepatorenal syndrome, hyponatremia, spontaneous bacterial peritonitis and hepatic hydrothorax) and both treatment regimens (nutrition and steroids). An overall assessment on subject compliance with each SOC will also be listed.

- Nutrition
 - Did subject have at least one Dietary Consult?
 - Was subject diagnosed with malnutrition?
 - Did subject receive nutritional supplements?
 - Did subject have hypocalcemia, hypomagnesemia, or hypophosphatemia?
 - Did subject receive metal supplements?
 - Did subject have any vitamin deficiencies?
 - Did subject receive vitamin supplements?
 - Overall assessment: was this subject compliant with Nutrition SOC?
- Steroids
 - Did subject receive Prednisone/ Prednisolone for at least 7 days?
 - Was treatment with steroids contraindicated?
 - Overall assessment: was this subject compliant with Steroids SOC?
- Ascites
 - Was subject diagnosed with ascites?
 - Subject underwent a paracentesis if clinically indicated either during screening or after randomization.
 - Ascitic fluid analysis, if clinically indicated, included relevant lab tests (e.g., cell count and differential and if indicated, ascitic fluid cultures)?
 - Diuretics were administered if clinically indicated?
 - Subjects with tense ascites (as assessed by investigator) underwent a paracentesis?
 - Subjects with refractory ascites (as assessed by investigator) underwent a paracentesis followed by oral diuretics?
 - Subjects who had >5 liters of ascitic fluid removed received albumin?

- Overall assessment: was this subject compliant with Ascites SOC?
- Gastroesophageal Varices
 - Was subject diagnosed with gastroesophageal varices?
 - Was the subject diagnosed to have gastroesophageal varices who had no previous history of gastroesophageal bleeding treated with either non-selective beta-blockers, endoscopic venous ligation, endoscopic sclerotherapy, or TIPS?
 - Were subjects who had active bleeding within 2 weeks prior to randomization given an antibiotic?
 - Did subjects who had a variceal bleed during screening or after randomization receive blood transfusions, antibiotics, and pharmacologic therapy (e.g., vasopressin, terlipressin) if clinically indicated?
 - Did subjects who had persistent or recurring gastroesophageal bleeding undergo an endoscopic variceal ligation (EVL)/sclerotherapy or a transjugular intrahepatic portosystemic shunt (TIPS)?
 - Were subjects who had a recurrent variceal bleed after randomization despite EVL or non-selective β -blockers treated with both EVL and non-selective β -blockers?
 - Overall assessment: was this subject compliant with Gastroesophageal Varices SOC?
- Hepatic Encephalopathy (HE)
 - Was subject diagnosed with HE?
 - If subject was diagnosed with HE, was subject treated with Lactulose and/or Rifaximin?
 - Overall assessment: was this subject compliant with Hepatic Encephalopathy SOC?
- Hepatorenal Syndrome (HRS)
 - Was subject diagnosed with HRS?
 - If subject had Type I HRS, was subject treated with a regimen consisting of at least one of the following medications: albumin, octreotide, and/or midodrine, or a regimen of at least one of the following medications: terlipressin and albumin?
 - Overall assessment: was this subject compliant with HRS SOC?
- Hyponatremia
 - Did subject have hypovolemic hyponatremia after Randomization?

- If subject had hypovolemic hyponatremia, was subject treated with fluids, and were diuretics discontinued?
- Did subject have hypervolemic hyponatremia after Randomization?
- If subject had hypervolemic hyponatremia, was subject treated with fluid restriction (if clinically indicated)?
- Overall assessment: was this subject compliant with Hyponatremia SOC?
- Spontaneous Bacterial Peritonitis (SBP)
 - Was subject diagnosed with SBP, culture-negative neutrocytic ascites, or monomicrobial nonneutrocytic bacterascites after Randomization?
 - If subject was diagnosed with SBP, etc., was subject treated with antibiotics?
 - Did subject have a prior episode of SBP?
 - If subject had a prior episode of SBP, was subject treated with long-term antibiotic prophylaxis?
 - Overall assessment: was this subject compliant with SBP SOC?
- Hepatic Hydrothorax
 - Did the subject have hepatic hydrothorax?
 - Was treatment administered if clinically indicated to treat hepatic hydrothorax?
 - Overall assessment: was this subject compliant with hepatic hydrothorax SOC?

